FCSA	Italian Federation of Thrombosis Centres (Federazione Centri per la diagnosi della trombosi e la Sorveglianza delle terapie Antitrombotiche)
FDA	Food and Drug Administration
GCP	Good Clinical Practice
LC-MS/MS	Liquid chromatography-tandem mass spectrometry
NVAF	Non Valvular Atrial Fibrillation

1. Background Information and rationale

Oral anticoagulant therapy is recommended in many clinical conditions to treat and prevent venous and arterial thromboembolism. Until a few years ago, vitamin K antagonists (VKA) were the only available drugs that, owing to their pharmacological characteristics, require frequent laboratory monitoring and expert dose adjustment (1). The direct oral anticoagulants (DOAC) have been introduced in clinical practice for the prevention of stroke and systemic embolism in patients with non-valvular atrial fibrillation (NVAF) and for the prevention and treatment of venous thromboembolism (2-5). Contrary to VKA, DOACs have been proposed without the need for laboratory testing and dose-adjustment because phase III clinical trials showed efficacy and safety at fixed dose based only on clinical criteria (2-6). Nevertheless, DOAC inter-individual variability has been evaluated in previous studies, and a high inter-individual variability has been demonstrated with all DOAC at different dosages. Furthermore, post-hoc analysis and FDA reports of RE-LY, Rocket and Hokusai trials (7-13) showed that plasma concentrations of dabigatran, rivaroxaban, and edoxaban were associated with the relative risk of bleeding and thromboembolic complications, suggesting that DOAC measurements could be clinically relevant for increasing safety and efficacy of these treatments. As a consequence, an open clinical question is if, in real world patient population, measurements of DOAC levels are associated with subsequent bleeding and/or thromboembolic events.

The guidelines of the Italian Federation of Thrombosis Centres (Federazione Centri per la diagnosi della trombosi e la Sorveglianza delle terapie Antitrombotiche, FCSA) (14) suggest to do follow-up visits after 1 month from the first therapy prescription, and later every 3-6 months, to assess the patient's compliance with treatment (since a low adherence rate could diminish the benefit of treatment), to investigate regarding the occurrence of thromboembolic and bleeding complications potentially related to the prescribed DOAC, and any new co-medications with possible drug-drug interactions, and to perform a blood sampling for the necessary exams (15, 16). The execution of specific laboratory tests after 15-30 days gives a DOAC level at the steady-state.

2. Study objectives

The MAS Study is an observational, multicentre, prospective cohort study in NVAF patients treated with one of the DOACs available in Italy for NVAF patients.

The general aim is to deepen the knowledge of DOAC treatment in NVAF patients, by measuring the plasma concentration of anticoagulant drugs and their correlation with any adverse events that may occur during treatment.

The study has an exclusively observational purpose in order to be the starting point for collaborative clinical studies, enabling their planning and execution; it is not aimed to influence the treatment of the individual patients included in the study.

The primary study objective is to evaluate the possible relationship between DOAC anticoagulant levels at the trough, measured at steady state (within the first 2-4 weeks of treatment) and occurrence of bleeding and thromboembolic events during the subsequent one year follow up.

3. Investigational plan

3.1 Study design

The MAS Study is an observational, prospective cohort study, double blind, multicentre, international and no Profit.

3.2 Setting

Anticoagulation clinics, affiliated or not to the Italian FCSA, will be asked to take an active part in the study, provided they have the facilities for blood sampling and processing.

3.3 Study population

4000 consecutive NVAf outpatients, 1000 for each single drug, aged >18 years and starting anticoagulation with one of the four DOAC (apixaban, dabigatran, edoxaban, rivaroxaban) will be enrolled at the moment of the first prescription. Patients will receive the type and dosage of DOAC on the base of clinical characteristics at the discretion of the attending physician, as the normal clinical practice, and the study will not influence the decision of the type and dosage of DOAC.

3.3.1 Inclusion criteria

- NVAf patients starting DOAC anticoagulation
- age > 18 years
- ability to give written informed consent
- availability, as part of the normal withdrawals, to the blood sampling for the study purpose
- availability for 12-months follow-up

3.3.2 Exclusion criteria

- age < 18 years
- indication for electrical cardioversion at the moment of drug prescription
- participation in Phase II or III clinical trials
- indication for treatment different from NVAf
- not suitable to give or not giving informed consent
- not available for blood collection or follow-up

4. Study procedures

4.1 Enrolment procedure

The active participants will propose to participate in the study to the NVAf subjects treated with DOAC that satisfy the inclusion and exclusion criteria

4000 consecutive NVAf patients, 1000 for each single drug, aged >18 years and starting anticoagulation with one of the four DOAC (apixaban, dabigatran, edoxaban, rivaroxaban) will be enrolled at the moment of the first prescription. The enrolment will end at the achievement of 4000 patients, 1000 for each drug.

The study requires a mandatory plasma collection for the measurement of the anticoagulant activity of the drug at the steady state, that is within the first 2-4 weeks of treatment, obtained at the time of trough, immediately before the subsequent intake of the drug. It is up to the participating centres, depending on their availability and organization, to perform an additional plasma collection on the same day 2 hours after the last intake, or to make further blood sampling after 3, 6 or 9 months from the time of the first prescription.

The Italian FCSA guidelines recommend a follow-up visit approximately one month after the first prescription to confirm the necessary patient's adherence to the treatment and to complete the routine exams not available at the time of prescription. On that occasion, and together with the routine blood sampling, it will be collected the plasma needed to measure the DOAC concentration for the study, taking 10 ml more of blood. Samples will be treated and identified locally in order to

maintain patient's anonymity, later they will be centralized to the Biobank of Fondazione Arianna Anticoagulazione in Bologna (Italy). Afterwards, samples will be distributed to laboratories identified by the Promoter for the measurement of DOAC plasma concentration. Test results will be centrally stored and communicated to the patient's recruiting centre only at the end of the study. Each patient will have a 12-month follow-up period, that will start at the time of the plasma collection, established within 15-30 days from the beginning of DOAC treatment.

The end of the study is at the conclusion of the 12-month follow-up of the last enrolled patient. In the 12 months following the end of the follow-up period of the last enrolled patient, all the data will be collected and the statistical analysis and the drafting of the final report will be carried out. All patients with NVAF who start DOAC treatment for the first time and meet the inclusion criteria are eligible for the study.

The investigator, after collection of the patient's informed consent, will collect and record in a specific electronic database (electronic CRF), the essential information collected during the routine checks performed within the previous 60 days.

The following data will be registered in the electronic CRF: patient identification number, date of birth, gender, blood cell count, creatinine, liver enzymes, diabetes, previous stroke/TIA, other comorbidities, concomitant medications (with a special attention to antiplatelet drugs), and past clinical history. The CHADS₂VASC and the HASBLED score will be calculated for all patients.

A unique anonymous identifying code will be given to each patient to ensure anonymity, which will be used both to collect clinical information and to identify biological samples. The investigator of the participating centre has to keep the correspondence between the patient's personal details and the related identification code (Appendix 1).

All events occurring during the 12-month follow-up will be recorded.

Data entered in the eCRF will be stored in the database located at a server of the S. Orsola-Malpighi University Hospital in Bologna, which, thanks to an agreement between Fondazione Arianna Anticoagulazione and the S. Orsola-Malpighi Hospital, guarantees the storage, backup and maintenance of the database.

An Adjudication Committee will evaluate the adverse events occurring during the year of follow-up, examining a possible correlation with the anticoagulant activity of the drug, measured in the sample taken at the entry of the study.

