4.2 Follow-up procedure

The follow-up of patients will last 12 months after blood sampling, also in patients that will stop anticoagulant treatment. In that case, a telephone follow-up is scheduled, to assess the patient's health status. A structured follow-up, as defined by FCSA guidelines, including clinical evaluation at the moment of blood sampling and each 3 to 6 months thereafter is required, in order to assess the patient's adherence to the treatment and compliance. During the follow-up, bleeding (major and clinically relevant non-major) and thromboembolic complications (Appendix 2) will be registered. Patients not referring at established dates are promptly looked for, to avoid as much as possible, lost at follow-up.

Clinical follow up will be performed each 3 to 6 months, and the following data will be registered: weight, blood pressure, change in clinical and health status and co-medications, creatinine clearance, blood cell count, liver enzymes. The need for an adequate adherence to the treatment will be stressed to each patient on every contact occasion; on these occasions, adherence to the treatment will be evaluated by a questionnaire according to the "Morisky medication adherence scale" (25, 26), given to the patient and to be completed by the patient himself. The negative

answer to all four questions in the questionnaire indicates a good adherence to the treatment, while the presence of even one positive answer suggests criticality in the adherence to therapy (26).

What is required to do during follow up should be in line with the indications for local and usual care management. In patients discontinuing anticoagulant treatment for whatever reason before the end of the follow-up period, a form detailing reason for discontinuation should be completed in the eCRF. Any surgical interventions or invasive procedures resulting in temporary therapy interruption (for at least 2 days) with no DOAC administration must be reported in the eCRF.

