All the dedicated methods available (from all the companies) will be assessed in laboratories identified by the Promoter to measure the anticoagulation level of the four direct oral anticoagulant drugs. Each assay, for all collected samples, will be carried-out in the same laboratory for that assay (to avoid inter-laboratory variability). The tests will be carried out when

appropriate in relation to the optimal number of samples to be tested. Results of the tests will be kept blind both to attending clinicians and patients; they will be open to the participating centre only at the end of follow-up period.

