5.2 Outcomes during the follow-up

5.2.1 Primary outcomes

1. Bleeding complications (Appendix 2): a composite of:
 - Major bleeding (ISTH definition) (17)
 - Clinically relevant non-major bleeding (18)
2. Thromboembolic complications (Appendix 2):
 - objectively documented cerebral vascular event
 - systemic embolism with angiographic demonstration of abrupt arterial occlusion
3. Mortality (cardiovascular and total)

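### Section 4.1 has the Adjudication Committee evaluate events while examining their correlation with the entry drug level; nothing blinds it to levels or requires classification to be final first

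*Combined protocol and SAP*

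**What the plan says.** Section 2 makes the trough level the exposure. The primary objective is "to evaluate the possible relationship between DOAC anticoagulant levels at the trough, measured at steady state", and the occurrence of bleeding and thromboembolic events in the following year.

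Section 4.1 gives the Adjudication Committee its task in one sentence: "An Adjudication Committee will evaluate the adverse events occurring during the year of follow-up, examining a possible correlation with the anticoagulant activity" of the drug, as measured in the sample taken at study entry.

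Four other places deal with blinding:

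- Section 3.1 calls the study "observational, prospective cohort study, double blind, multicentre, international and no Profit" and does not say who is blinded, or to what.
- Section 4.1 releases test results to the "recruiting centre only at the end of the study".
- Section 5.1 says: "Results of the tests will be kept blind both to attending clinicians and patients".
- Section 8.1 has event data sent blind to the Safety Committee, without saying blind to what.

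Section 5.3 has events and their possible relationship with individual entry levels reported to the Safety Committee every six months. Section 6.3 already plans the analysis of events against drug levels.

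**The concern.** The body that decides whether an outcome occurred is told, in the same sentence, to look at its relation to the exposure. If levels are known when an event is classified, outcomes that depend on judgement can be misclassified differently at high and low levels. Section 6.2 states the expected directions: more thromboembolism in the lowest class and more bleeding in the highest. A level-aware error in those two outcomes could therefore run towards the hypothesis and produce or inflate the association that the study is meant to estimate.

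**Working it through.** **1. Who is blinded.** The plan gives no figure on this point, so the first check compares the texts.

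| Section | Party covered | Adjudication Committee covered? |
|---|---|---|
| 3.1 | None named | Not stated |
| 4.1 | Recruiting centre | No |
| 5.1 | Attending clinicians, patients | No |
| 5.3 | Safety Committee, which receives events in relation to levels | No |
| 8.1 | Safety Committee, sent event data blind | No |

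Sections 6.2 and 6.3 and Appendix 2 contain no rule on blinded adjudication or on the order of classification and linkage.

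**2. Which outcomes are exposed.**

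- *Clinically relevant non-major bleeding* is part of the primary bleeding composite (section 5.2.1). Its last criterion in Appendix 2 is open and turns on whether a bleed is considered to have had clinical consequences.
- *Fatal bleeding* is defined in Appendix 2 by the committee's own determination that bleeding caused or contributed to the death. It is also one of the criteria for major bleeding.
- *Cerebral vascular event* is exposed to a lesser degree. Section 5.2.1 requires objective documentation, but neither that section nor Appendix 2 defines the event further.
- *Cause of death* depends on judgement and feeds cardiovascular mortality, but the documents state no expected direction for mortality by level.
- *Major bleeding on haemoglobin, transfusion or site criteria* is less exposed. *Total mortality* is not exposed.

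**3. Which way bleeds can move.** Raising a minor bleed to clinically relevant is possible only if minor bleeds reach the committee. Section 4.1 says "All events occurring during the 12-month follow-up will be recorded", whereas section 4.2 says "bleeding (major and clinically relevant non-major) and thromboembolic complications (Appendix 2) will be registered", which leaves minor bleeding out. Rejecting a reported bleed does not depend on this, but the breadth of the open criterion leaves limited room to do so.

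**4. Illustration of size.** Inputs from section 6.2: overall bleeding of about 10% per year and 1000 patients per drug. Four equal classes would hold 1000/4 = 250 each.

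Assumptions, not in the documents:

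- no true effect, so 10% bleeding in both extreme classes;
- a share f of 25% or 50% of composite bleeds depends on judgement;
- a fraction u of 10% or 20% of those is shifted.

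The net relative shift is s = f × u:

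- 0.25 × 0.10 = 0.025
- 0.25 × 0.20 = 0.50 × 0.10 = 0.05
- 0.50 × 0.20 = 0.10

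A shifted lowest class has rate 0.10 × (1 − s). A shifted highest class has rate 0.10 × (1 + s). The probability that the pooled two-proportion z exceeds 1.96 towards more bleeding in the highest class was found by exact enumeration of the two binomials. With no shift it is 2.4%.

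| s | Both shift (ratio) | Lowest only (ratio) | Highest only (ratio) |
|---|---|---|---|
| 0.025 | 3.7% (1.05) | 3.0% (1.03) | 3.0% (1.03) |
| 0.05 | 5.5% (1.11) | 3.7% (1.05) | 3.7% (1.05) |
| 0.10 | 11.0% (1.22) | 5.6% (1.11) | 5.4% (1.10) |

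Ratios are highest to lowest; for example, with both classes shifted at s = 0.10, 0.11/0.09 = 1.22.

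Section 6.2 divides the range of levels, so the classes may be unequal. With 400 patients in the lowest class and 100 in the highest, no shift gives 2.9%, and opposite shifts give 4.1%, 5.7% and 10.2%.

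**The case against.** The strongest reply is that the sentence in section 4.1 is compatible with sound practice: the committee could classify first and examine correlation afterwards. Section 5.3 sends level data to the Safety Committee, not to adjudicators. Section 5.1 has assays run when enough samples are available, so a level may not exist when an event is reviewed. Clinicians, patients and centres are blind, so detection and reporting are protected. All of this stands, and it limits the point to central classification. It does not remove the point: nothing requires that order, and section 5.3 expects event-by-level data every six months during the study.

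A second reply is that the double-blind label, or the blind transfer in section 8.1, already covers the committee. The label names no one. Section 8.1 concerns the Safety Committee, and blind there may mean only de-identified. It might also be a loose reference to blinded event assessment, but the documents do not say whether the two committees are the same or overlap, and section 5.3 gives the Safety Committee information on individual levels. Whether sections 5.3 and 8.1 conflict cannot be settled from the text.

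Third, the shift sizes have no source in the documents. That is right. The 11.0% needs the largest value of both assumptions and opposite shifts in both extreme classes, and its upward part needs minor bleeds to reach the committee. If few bleeds depend on judgement, or only one class shifts, the effect is small.

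Two stronger readings are tempting. A reader might infer that adjudicators will see levels before classifying, so that the primary association will be biased. The wording permits that but does not state it. A reader might also infer that cardiovascular mortality would be biased towards the hypothesis. Section 6.2 gives directions only for thromboembolism and bleeding, so no such direction can be claimed for mortality.

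**Conclusion.** The point holds as a missing safeguard, made more important by a remit that joins outcome evaluation to the exposure. It is not evidence that bias will occur. It bears mainly on clinically relevant non-major bleeding and fatal bleeding, less on cerebral vascular events, and without a stated direction on cause of death.

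Under the stated assumptions, the chance of a false finding of more bleeding in the highest class moves from 2.4% to between 3.0% and 11.0%. This shows what is possible and does not set the severity. The case for change rests on the wording of section 4.1, the absence of any rule elsewhere, and the small cost of adding one. It is a cheap improvement.

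**What to change.** **Section 4.1.** Replace the Adjudication Committee sentence with:

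> An Adjudication Committee will classify every reported event against section 5.2.1 and Appendix 2 without access to drug levels or level class. Levels are linked to events for analysis only after classification is final.

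Section 5.2.1 must be cited as well as Appendix 2, because the appendix defines neither cerebral vascular event nor systemic embolism. No analysis is lost, since the correlation work stays in section 6.3.

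**Section 5.3.** State that level-by-event data prepared for the Safety Committee are not available to anyone adjudicating an event before its classification is final. State whether the two committees share members.

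**Section 8.1.** State what blind means, so that it can be reconciled with section 5.3.

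**Events already classified.** If any event was classified with its level known, re-adjudicate it blind. The documents do not show that this has happened.

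**Cost.** Small: a wording change and a restriction on data access. Section 4.1 already has results stored centrally. The documents do not give the committee's membership or its data access, so the sponsor should confirm that the restriction is workable. The Safety Committee's remit is unchanged.

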4.2 Follow-up procedure

The follow-up of patients will last 12 months after blood sampling, also in patients that will stop anticoagulant treatment. In that case, a telephone follow-up is scheduled, to assess the patient's health status. A structured follow-up, as defined by FCSA guidelines, including clinical evaluation at the moment of blood sampling and each 3 to 6 months thereafter is required, in order to assess the patient's adherence to the treatment and compliance. During the follow-up, bleeding (major and clinically relevant non-major) and thromboembolic complications (Appendix 2) will be registered. Patients not referring at established dates are promptly looked for, to avoid as much as possible, lost at follow-up.

Clinical follow up will be performed each 3 to 6 months, and the following data will be registered: weight, blood pressure, change in clinical and health status and co-medications, creatinine clearance, blood cell count, liver enzymes. The need for an adequate adherence to the treatment will be stressed to each patient on every contact occasion; on these occasions, adherence to the treatment will be evaluated by a questionnaire according to the "Morisky medication adherence scale" (25, 26), given to the patient and to be completed by the patient himself. The negative

answer to all four questions in the questionnaire indicates a good adherence to the treatment, while the presence of even one positive answer suggests criticality in the adherence to therapy (26).

What is required to do during follow up should be in line with the indications for local and usual care management. In patients discontinuing anticoagulant treatment for whatever reason before the end of the follow-up period, a form detailing reason for discontinuation should be completed in the eCRF. Any surgical interventions or invasive procedures resulting in temporary therapy interruption (for at least 2 days) with no DOAC administration must be reported in the eCRF.

4.3 Definition of the conclusion of the study

The study will be concluded for each patient at the end of the 12-months follow-up and, globally, at the completion of the last follow-up of the last patient enrolled

5. Study evaluations and measurements

